### **11.4 Additional Analyses**

**Baseline Characteristic Analyses:** Qualitative baseline characteristics will be summarized with the number and percent of subjects in each treatment group with the characteristic. Quantitative characteristics (e.g., age, height, and weight) will be summarized with the median, mean, standard deviation, minimum value, and maximum value. Categorical characteristics will be tabulated.

The number and percent of subjects, who are randomized, treated with randomized study drug, prematurely discontinued study drug, are lost to follow up, and completed four 12 week cycles of follow-up after randomization will be summarized.

The number and percent of subjects with each medical history will be summarized. Fisher's exact test will be used to assess treatment group differences in the proportions of subjects with each medical history. The number and percent of subjects that receive each medication that is not the study drug will be summarized.

There will be no adjustment for multiple statistical comparisons. We recognize that carrying out multiple significant tests increases the risk of false positive results among the collection of all analyses. Therefore, except for the primary outcome, all other analyses are considered as secondary, tertiary, or exploratory.

**ECOG Performance Status:** ECOG Performance Status will be captured as on a 6-point categorical scale from 0 (normal activity) to 5 (dead) and summarized using shifts from baseline to the 24-week and 48-week evaluations. Baseline is defined as the last ECOG value prior to or on the date of randomization. The percentage of patients with an increase of at least 1 point from baseline will be presented for each treatment group at both the 24-week and 48-week evaluation time points.

**Adherence:** Participants who completed 4 cycles of study and had at least 80% of intake of the planned consumption will be defined as study compliant. An overall probability of study compliance will be estimated with a 95% confidence interval. The difference in proportion of compliance between two groups will be tested using Fisher's exact test at a two-sided alpha level of 0.05. Summary statistics will also be provided for the time from the first dose to the last dose of study drug.

**Food Frequency Questionnaire and Dietary Supplement List:** The categories of "how often you ate the food" on the food questionnaire will be summarized with frequencies and percentages for both treatment groups at baseline and at each visit (12, 24, 36, 48 weeks and progression). A nutrient analysis by the Nutrition Assessment Shared Resource at the Fred Hutchinson Cancer Research Center will provide estimates of daily intake of key antioxidants over the course of the study and will be summarized descriptively by treatment group. Baseline is defined as the last questionnaire completed prior to or on the date of randomization. Provided missing data are minimal, a sensitivity analysis of the primary endpoint may be done by adjusting for the estimated daily antioxidant intake of patients over the course of the study. The dietary supplement list will be used to further document the comparability of the treatment arms. The list of supplements was selected from the NIH. In case of a large discrepancy, this may also be used as a covariate in a sensitivity analysis.

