### **5.1 MPX Administration**

Each treatment cycle is 12 weeks (84 days). Patients will take 8 MPX pills or 8 placebo pills daily, for once daily oral dosing of 4000 mg MPX. Patients may continue to receive additional cycles of study drug and will be followed every 12 weeks with standard visits with their physician until completion of 48 weeks of study treatment, disease progression, or until they wish to discontinue the drug.

Patients will self-administer the assigned number of capsules on a daily schedule. Patients will return capsule containers and any unused study drug to the study coordinator or research nurse at each scheduled follow-up visits. Returns will be documented on the drug accountability log by the pharmacist or pharmacist designee.

Compliance with study product consumption will be evaluated by subject interview and by patient pill diaries (Appendix B) that will be collected at each visit. Compliance will be recorded as a percent of scheduled intakes of study product consumed. Non-compliance will be defined as consumption of <80% of the scheduled intakes of study product.

Patients will be asked to refrain from adding other vitamin or herbal supplements during the study period and follow-up. If a patient does not comply, he will first be counseled that he may be withdrawn from the study. If he persists in taking vitamins or herbal supplements, he will be withdrawn from the study.

Participants will be encouraged to administer the MPX capsules as follows:

- 1) MPX Capsules must be swallowed whole
- 2) MPX Capsules should be taken with water
- 3) MPX capsules should be taken at least 60 minutes prior to eating or 2 hours after eating
- 4) Ingestion of capsules may be spread out over 2 hours if necessary
- 5) Vomited doses will not be made up. If the vomiting occurs after 3 sequential doses and is thought to be related to study drug, the patient should refrain from taking additional MPX capsules and report this to study team.
- 6) If a dose is missed (forgotten at the usually administered time), it may be made up any time later that same day.

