### **5.2 Blinding**

The double-blind portion of the study will end when every subject has either completed the study, been treated for 48 weeks, or discontinued the study. A subject is considered to have completed the study if he experiences PSA progression as defined in section 5.4. A subject will also be considered to have completed the study if they have not experienced PSA progression but remain on-study at the time the study ends at 48 weeks. Patients will not be informed if they are on the MPX or placebo arm. At protocol defined progression or completion of 48 weeks of treatment, patients will be offered an additional four 12-week cycles of MPX treatment, and will come for a visit every 12 weeks, without correlates but with PSA drawn every 12 weeks. Patients who come off study for any other reason will not be offered open label, extension MPX. Subjects will have an end of study visit and are required to have CT and bone scans prior to beginning the open label extension, and at discharge.

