### **5.4 Definition of Treatment Response and Disease Progression**

**Objective Response (OR):** Defined as a decrease of 50% or more in the PSA compared with the baseline level, confirmed by a second PSA at least 3-4 weeks later.

**Progressive Disease (PD):** Defined as:

- Radiographic Progression  
Radiographic progression for soft tissue lesions will be determined using RECIST 1.1. Radiographic progression for bone lesions will be determined by radionuclide bone scan using the consensus guidelines of the PCWG2 criteria, Or
- Unequivocal clinical progression: physical symptoms felt to be cancer related (in the opinion of the investigator), Or
- PSA Progression: Clinically significant increase in PSA as defined below.
  - *For subjects whose PSA declined from baseline (week 1 day 0):* record time from start of therapy to first PSA increase that is  $\geq 50\%$  and  $\geq 5$  ng/mL above the nadir, and which is confirmed by a second value  $\geq 3$  weeks later.
  - *For subjects whose PSA has not declined from baseline:* PSA progression has occurred if both:  
There has been a  $> 50\%$  increase over baseline (week 1 day 0), AND  
The value of PSA is  $> 5$  ng/mL above the baseline (week 1 day 0) value after 12 weeks

If subject's PSA progresses  $\geq 50\%$  and  $\geq 5$  ng/mL above the baseline (week 1 day 0) on Week 12, repeat the PSA at Week 14-16 to confirm rise. Subjects should continue taking study drug during this period, until the rise is confirmed. Once confirmed, subjects should either schedule Discontinuation Visit or start Open Label Extension treatment.

**Stable Disease (SD):** Disease Assessment that does not qualify as either objective response or progressive disease.

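### Section 11.4 classes a man who took every capsule until protocol-defined progression as non-compliant, so the between-arm adherence test is confounded by progression

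*Combined protocol and SAP*

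**What the plan says.** The Adherence paragraph of section 11.4 sets two joint conditions: "Participants who completed 4 cycles of study and had at least 80% of intake of the planned consumption will be defined as study compliant". It gives no exception for progression and does not say whether planned consumption covers the full 48 weeks or only the time a man was due to be on drug. The proportions in the two arms are compared by Fisher's "exact test at a two-sided alpha level of 0.05". Duration of dosing is descriptive only: "Summary statistics will also be provided for the time from the first dose to the last dose of study drug".

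Section 5.1 sets a cycle at 12 weeks and continues blinded treatment "until completion of 48 weeks of study treatment, disease progression, or until they wish to discontinue the drug". Section 5.4 says of a PSA rise: "Once confirmed, subjects should either schedule Discontinuation Visit or start Open Label Extension treatment". Section 5.5 lists disease progression among the reasons for removal.

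Two other sections classify the same man differently. Section 5.1 uses intake alone: "Non-compliance will be defined as consumption of <80% of the scheduled intakes of study product". Section 5.2 states: "A subject is considered to have completed the study if he experiences PSA progression as defined in section 5.4".

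**The concern.** A man who follows the protocol exactly, takes all his capsules and comes off blinded drug because his progression is confirmed at, say, week 24 fails the section 11.4 definition. He is compliant under section 5.1 and, if he progressed by PSA, a completer under section 5.2. Three sections give two answers for one man.

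The consequence lies in the comparison of arms. The trial's hypothesis is that MPX slows the rise in PSA, and rise in PSA drives progression. If the hypothesis is true, more placebo men leave before week 48 and placebo compliance looks worse, although capsule-taking may be the same. Readers use adherence to judge whether a result reflects exposure to the product. Here the adherence measure is partly an outcome.

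**Working it through.** **Definition applied to one man.** Four cycles × 12 weeks = 48 weeks. A man who stops at week 36 for progression has completed three cycles and fails the first condition with 100% intake. If planned consumption means 48 weeks, he fails the second as well: 80% of 48 weeks is 38.4 weeks, and 36/48 = 75%.

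**Plan's own figure.** The adherence paragraph states none. The slopes and SD used below are those behind the primary power (section 11: slopes 0.033 on MPX and 0.083 untreated, SD 0.075). With 39 per arm, a difference of 0.05 and two-sided alpha 0.05, the normal formula gives power 0.837 and a noncentral-t ANCOVA with no pre/post correlation gives 0.828. The stated 83% is reproduced.

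**Fisher test with assumed exits.** Inputs: 40 men per arm (section 5), every man a perfect capsule-taker, so the proportion compliant is 1 − exit proportion. The rejection probability is the sum, over all pairs of counts (a, b) with two-sided Fisher p ≤ 0.05, of Bin(a; 40, p_MPX) × Bin(b; 40, p_placebo).

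| Exit before week 48, placebo / MPX (assumed) | Compliant, placebo / MPX | Fisher rejects |
|---|---|---|
| 10% / 5% | 90% / 95% | 4.3% |
| 30% / 15% | 70% / 85% | 28.1% |
| 50% / 25% | 50% / 75% | 55.9% |

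**Which exits are plausible.** For men whose PSA has not declined, section 5.4 requires a rise of more than 50% and of more than 5 ng/mL over baseline. With baseline PSA B, the value must exceed r = max(1.5, 1 + 5/B) times baseline. The last scheduled PSA before four cycles are complete is at week 36, which is 36 × 7 / 30.44 = 8.28 months. The slope needed is t = ln(r)/8.28, and the probability of reaching it is 1 − Φ((t − mean)/0.075). Baseline PSA is assumed, because the documents give none.

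| Baseline PSA (ng/mL) | r | t per month | Progressed by week 36, placebo / MPX | Fisher rejects, intake 100% in both arms | Fisher rejects, 90% truly adherent in both arms |
|---|---|---|---|---|---|
| 0.5 | 11 | 0.290 | 0.3% / 0.0% | 0% | 1.7% |
| 1 | 6 | 0.216 | 3.8% / 0.7% | 0.3% | 3.0% |
| 2 | 3.5 | 0.151 | 18% / 6% | 28% | 17% |
| 5 | 2 | 0.084 | 50% / 25% | 55% | 45% |
| 10 | 1.5 | 0.049 | 67% / 42% | 58% | 49% |

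The 5 ng/mL condition drives this table: men with low PSA can hardly meet it within 36 weeks.

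**No difference in progression.** If the arms progress equally, rejection stays at or below 3.3%, but the reported level is too low. With 90% true adherence and 10% progression, 0.90 × 0.90 = 81% is reported.

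**Same check with progression not counted against a man.** With 90% adherence in both arms the proportions are 90% and 90%, and Fisher rejects in 1.7% of trials whatever the progression rates.

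**The case against.** A reader might infer that the between-arm test simply measures progression. The documents do not support that. The section 11.4 definition also fails men whose intake is below 80% and men who stop for toxicity, new illness or their own wish. Progression is one component, and it dominates only if it is common before week 48 and differs by arm.

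A reader might also infer that any difference on this measure is spurious. That is too strong. If more men on MPX stop through intolerance or choice, lower persistence on MPX is a legitimate adherence result. The objection to the definition is confined to exits that the protocol itself prescribes at progression.

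Three further points have weight. First, sections 5.1 and 11.4 serve different purposes: one triggers counselling and withdrawal during conduct, the other summarises the whole trial. Different definitions are not in themselves an error, but this does not explain why a prescribed exit should count as non-compliance. Second, section 5.2 might be read as making PSA progressors completers for section 11.4 too. The wording there is four cycles, however, and the same section separately counts men who complete four 12-week cycles. At best the text is ambiguous, and section 5.2 does not cover radiographic or clinical progression. Third, section 11.4 already tabulates premature discontinuation and four-cycle completion, and section 11.2 compares time to PSA progression by arm. A careful reader could trace a compliance difference back to early exits. That softens the problem, but the test would still be reported on the composite.

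**Conclusion.** The definition contradicts section 5.1 and, for PSA progression, section 5.2. The Fisher test built on it is confounded by progression, with a bias towards higher compliance on MPX if the trial's hypothesis is true.

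The size cannot be fixed from the documents. It runs from practically nothing at baseline PSA of about 1 ng/mL or lower to rejection in more than half of trials at 5 ng/mL or above, with identical capsule-taking. Eligibility admits both ends: PSA just above 0.2 ng/mL after surgery, and radiation-only men at least 2 ng/mL above nadir. The percentages by baseline PSA are illustrative. The model ignores confirmation of the rise, PSA declines, and radiographic or clinical progression, and it treats the slope SD as true spread between men.

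The importance is minor. Section 11.4 classes everything except the primary outcome as secondary, tertiary or exploratory. The primary analysis is by intention to treat, and no efficacy population is built on this definition.

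**What to change.** Replace the sentence in section 11.4. Compute compliance as capsules taken divided by capsules scheduled up to the end of the man's protocol-scheduled blinded treatment (week 48 or protocol-defined progression), with at least 80% as the threshold. Apply Fisher's test to that. This states the denominator, removes progression as a cause of non-compliance, and aligns the rule with sections 5.1 and 5.2. A man who quits by choice after two weeks is still measured against 48 weeks, so he does not become compliant by leaving.

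Present the result beside the four-cycle completion and premature-discontinuation counts already planned in section 11.4, by arm and with reasons for stopping, so that voluntary and toxicity stops stay visible as persistence.

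The cost is about one sentence of text. Diaries and returned-pill counts are already collected, so no new data or visits are needed. The downside is that two figures, intake and persistence, must be read together instead of one composite.

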## APPENDIX A: ECOG PERFORMANCE STATUS SCALE

Grade	Descriptions
0	Normal activity. Fully active, able to carry on all pre-disease performance without restriction.
1	Symptoms, but ambulatory. Restricted in physically strenuous activity, but ambulatory and able to carry out work of a light or sedentary nature (e.g., light housework, office work).
2	In bed <50% of the time. Ambulatory and capable of all self-care, but unable to carry out any work activities. Up and about more than 50% of waking hours.
3	In bed >50% of the time. Capable of only limited self-care, confined to bed or chair more than 50% of waking hours.
4	100% bedridden. Completely disabled. Cannot carry on any self-care. Totally confined to bed or chair.
5	Dead

## **APPENDIX B: Study Drug Compliance - Pill Diary**

Patient should be provided with diary pages for 90 days, enough to log study drug compliance between study visits.

**J1823 The MAP TRIAL: A Randomized Double-Blind, Placebo-Controlled Study of the Effects of MPX Capsules on Rising Prostate-Specific Antigen Levels in Alanine/Alanine SOD2 Genotype Men Following Initial Therapy for Prostate Cancer**

Name \_\_\_\_\_ Subject's ID #: \_\_\_\_\_ Study Weeks# \_\_\_\_\_

- Take 8 capsules whole from the bottle once every day with water.
- Your pills should be taken **ONE** hour before food or **TWO** hours after food. You can take the capsules over a 2-hour period if needed.
- **Bring your diary and pill supply with you to each clinic visit. Return all unused pills and empty bottles.**
- Tell us the time of your last meal (CLINIC VISIT DAY ONLY): \_\_\_\_\_

Cycle Day	Date of Dosing	Time of Dose	# of Capsules	Comments/Side Effects
1				
2				
3				
4				
5				
6				
7				
8				
9				
10				
11				
12				
13				
14				
15				
16				
17				
18				
19				
20				

Cycle Day	Date of Dosing	Time of Dose	# of Capsules	Comments/Side Effects
21				
22				
23				
24				
25				
26				
27				
28				
29				
30				
31				
32				
33				
34				
35				
36				
37				
38				
39				
40				
41				
42				
43				
44				
45				
46				
47				
48				
49				
50				

Cycle Day	Date of Dosing	Time of Dose	# of Capsules	Comments/Side Effects
51				
52				
53				
54				
55				
56				
57				
58				
59				
60				
61				
62				
63				
64				
65				
66				
67				
68				
69				
70				
71				
72				
73				
74				
75				
76				
77				
78				
79				
80				

Cycle Day	Date of Dosing	Time of Dose	# of Capsules	Comments/Side Effects
81				
82				
83				
84				

Subject's signature: \_\_\_\_\_

Date: \_\_\_\_\_

Reviewer's signature: \_\_\_\_\_

Date: \_\_\_\_\_

## APPENDIX C: FOOD FREQUENCY QUESTIONNAIRE FOR FRUITS AND VEGETABLES

Subject ID ____ - ____ - ____      Initials ____      Study Weeks _____
Date of Visit: ____ / ____ / ____ (mm/dd/yy)

**Instructions: Answer each question as best you can – estimate if you are not sure.**

	Not in the last month	1 per month	2–3 per month	1–2 per week	3–4 per week	5–6 per week	1 per day	2+ per day	Medium serving size	Amount		
										S	M	L
FRUITS												
Example: Rice									$\frac{3}{4}$ cup			
Apples, applesauce									1 medium apple or $\frac{1}{2}$ cup			
Apricots									2 medium fruit			
Bananas									1 medium fruit			
Cantaloupe									$\frac{1}{4}$ melon			
Cherries									$\frac{1}{2}$ cup			
Grapefruit									1 medium fruit			
Grapes									$\frac{1}{2}$ cup			
Honeydew melon									$\frac{1}{4}$ melon			
Kiwi									1 medium fruit			
Limes or lemons									1 lemon/lime			
Mango									$\frac{1}{2}$ mango			
Nectarines									1 medium fruit			
Oranges									1 orange			
Papaya									$\frac{1}{4}$ papaya			

										Amount		
	Not in the last month	1 per month	2–3 per month	1–2 per week	3–4 per week	5–6 per week	1 per day	2+ per day	Medium serving size	S	M	L
Peaches									1 medium fruit or ½ cup			
Pears									1 medium fruit or ½ cup			
Pineapple									¼ fruit			
Plums									1 medium fruit			
Raisins									¼ cup or small pack			
Strawberries									½ cup			
Berries (Excluding strawberries)									½ cup			
Tangerines									1 tangerine			
Watermelon									¼ melon			
VEGETABLES												
Avocado									½ medium or ½ cup			
Broccoli									½ cup			
Brussel sprouts									½ cup			
Cabbage									½ cup			
Carrots									½ cup			
Cauliflower									½ cup			
Celery									½ cup			
Coleslaw									½ cup			
Corn									½ cup			
Greens (Swiss chard, kale,									½ cup			

											Amount		
	Not in the last month	1 per month	2–3 per month	1–2 per week	3–4 per week	5–6 per week	1 per day	2+ per day	Medium serving size	S	M	L	
collard, turnip, or mustard greens)													
Spinach (cooked)	○	○	○	○	○	○	○	○	½ cup	○	○	○	
Spinach (raw)	○	○	○	○	○	○	○	○	1 cup	○	○	○	
Fresh tomatoes	○	○	○	○	○	○	○	○	1 medium or 4 slices	○	○	○	
Green beans	○	○	○	○	○	○	○	○	½ cup	○	○	○	
Green peas	○	○	○	○	○	○	○	○	½ cup	○	○	○	
Green pepper	○	○	○	○	○	○	○	○	¼ cup	○	○	○	
Green salad (iceberg lettuce only)	○	○	○	○	○	○	○	○	1 cup	○	○	○	
Green salad (romaine or leaf lettuce)	○	○	○	○	○	○	○	○	1 cup	○	○	○	
Jalapeno, sweet red, or chili peppers	○	○	○	○	○	○	○	○	¼ cup	○	○	○	
Mixed vegetables (frozen or canned)	○	○	○	○	○	○	○	○	½ cup	○	○	○	
Onions and leeks	○	○	○	○	○	○	○	○	½ cup	○	○	○	
Summer squash or zucchini	○	○	○	○	○	○	○	○	½ cup	○	○	○	
Sweet potatoes or yams	○	○	○	○	○	○	○	○	½ cup	○	○	○	
CEREALS, GRAINS, NUTS, AND SNACKS													
Almonds	○	○	○	○	○	○	○	○	¼ cup	○	○	○	
Peanuts	○	○	○	○	○	○	○	○	¼ cup	○	○	○	
Other nuts (e.g., Brazil, pistachio)	○	○	○	○	○	○	○	○	¼ cup	○	○	○	
Peanut butter	○	○	○	○	○	○	○	○	2 Tbsp.	○	○	○	

										Amount		
	Not in the last month	1 per month	2–3 per month	1–2 per week	3–4 per week	5–6 per week	1 per day	2+ per day	Medium serving size	S	M	L
Cold cereal, fortified (e.g., Raisin Bran®)									1 cup			
Oatmeal (fortified, instant)									1 cup			
Whole wheat bread or rolls (enriched)									2 slices or 1 medium roll			
MEATS, EGGS, AND DAIRY PRODUCTS												
Liver (beef or chicken)									4 ounces			
Fish									4 ounces			
Cheese (excluding cottage and cream cheese)									1 slice, ¼ cup, shredded			
Cottage cheese									½ cup			
Cream cheese									2 Tbsp.			
Eggs, whole									1 medium			
Fat-free milk									8 oz. glass			
Reduced-fat milk									8 oz. glass			
Whole milk									8 oz. glass			
Soy milk									8 oz. glass			
MIXED DISHES AND SOUPS												
Chili									1 cup			
Macaroni and cheese									1 cup			
Minestrone									1 cup			
Pizza									1 slice of a 12" pizza			

										Amount		
	Not in the last month	1 per month	2–3 per month	1–2 per week	3–4 per week	5–6 per week	1 per day	2+ per day	Medium serving size	S	M	L
Spaghetti, lasagna, and other pasta with tomato sauce	○	○	○	○	○	○	○	○	1 cup	○	○	○
Stews with tomatoes	○	○	○	○	○	○	○	○	1 cup	○	○	○
Tomato soup	○	○	○	○	○	○	○	○	1 cup	○	○	○
Vegetable soup	○	○	○	○	○	○	○	○	1 cup	○	○	○
SAUCES, CONDIMENTS, AND OILS												
Butter or margarine	○	○	○	○	○	○	○	○	2 pats or 2 teaspoons	○	○	○
Mayonnaise, including low-fat	○	○	○	○	○	○	○	○	1 Tbsp.	○	○	○
Ketchup	○	○	○	○	○	○	○	○	2 Tbsp.	○	○	○
Tomato sauce (excluding pasta sauce)	○	○	○	○	○	○	○	○	½ cup	○	○	○
Salsa	○	○	○	○	○	○	○	○	1 Tbsp.	○	○	○
Olive oil	○	○	○	○	○	○	○	○	1 Tbsp.	○	○	○
Safflower or corn oil	○	○	○	○	○	○	○	○	1 Tbsp.	○	○	○
Soybean oil	○	○	○	○	○	○	○	○	1 Tbsp.	○	○	○
Wheat germ oil	○	○	○	○	○	○	○	○	1 Tbsp.	○	○	○
BEVERAGES												
Apple juice or cider	○	○	○	○	○	○	○	○	8 oz. glass	○	○	○
Carrot juice	○	○	○	○	○	○	○	○	8 oz. glass	○	○	○
Cranberry juice (or Cran-blend juice)	○	○	○	○	○	○	○	○	8 oz. glass	○	○	○
Grapefruit juice	○	○	○	○	○	○	○	○	8 oz. glass	○	○	○

										Amount		
	Not in the last month	1 per month	2–3 per month	1–2 per week	3–4 per week	5–6 per week	1 per day	2+ per day	Medium serving size	S	M	L
Fruit punch or lemonade									8 oz. glass			
Orange juice, unfortified									8 oz. glass			
Orange juice (Vitamin C-fortified)									8 oz. glass			
Orange juice (Fortified, other)									8 oz. glass			
Pineapple juice									8 oz. glass			
Tea (Iced or Hot)									8 oz. glass			
Tomato juice or V-8									8 oz. glass			
Red Wine									5 oz. glass			

Please answer these two important questions.

	Never or less than once per week	1–2 per week	3–4 per week	5–6 per week	1 per day	2 per day	3 per day	4 per day	5+ per day
In summary, how often did you eat vegetables in the past month, not counting potatoes, salad, or beans?									
In summary, how often did you eat fruits in the past month, not counting juices?									

